11.3 Training

11.3.1 Research Team Training

The training of appropriate clinical site personnel will be the responsibility of the Sponsor or the Sponsor's representative. In some cases, training may be performed by an existing site staff member who has already been trained by the Sponsor (e.g., assigning a new CRC to the study).

Prior to initiating subject enrollment at a site, appropriate study training will be provided. To ensure uniform data collection and protocol compliance, the Sponsor will present a formal educational session to study site personnel that will include review of the Clinical Study Protocol, techniques for the identification of eligible subjects, instructions on in-hospital data collection, follow-up schedules, and regulatory requirements. Remote as well as on-site contacts will be used to monitor study performance indicators such as enrollment compliance, data submission rate, data errors, protocol questions, and GCP compliance. The sponsor will reinforce the training or provide clarification throughout the study, as needed.

11.3.2 Investigator Training

Prior to initiating subject enrollment at a site, appropriate study training will be provided. Investigators selected to participate in the study will be experienced in intracardiac mapping and AF ablation with focal ablation catheters. In addition to research team training outlined above, Investigators will undergo didactic and hands-on device (VARIPULSE™ Catheter and TRUPULSE™ Generator) training in accordance with the physician training charter.

12. Study Medications

12.1 Antiarrhythmic Drugs

12.1.1 Definitions

- Antiarrhythmic drugs (AADs)

The study protocol will classify and analyze the following:

- Class I drugs (e.g., flecainide, propafenone, disopyramide, etc.)
 - Class III drugs (e.g., amiodarone, dronedarone, dofetilide, etc.)

- Previously Failed AAD

Any AAD that a subject has ever taken for the treatment of his/her AF, prior to enrollment, is considered a “previously failed AAD” if it meets both of the following conditions:

- prior to enrollment, the AAD was ineffective in controlling the subject’s AF or produced intolerable side effects leading to its discontinuation.
 - the AAD is administered for AF

- Contraindicated AAD

Any AAD contraindicated in the subject due to known medical conditions. The reason for contraindication MUST be documented for each subject

- New AAD

ANY AAD that was never taken for the treatment of AF prior to enrollment is considered a “new AAD” if the drug is administered to treat atrial tachyarrhythmia episodes post-enrollment.

Table 12.1.1.1 illustrates the corresponding status of primary effectiveness endpoints based on AAD therapy administered in the blanking and post-blanking periods.

Table 12.1.1.1: AAD Usage and Impact on Primary Effectiveness Classification

	Through Three-Month Follow-Up Visit Window (0-104 days post procedure)	Post-Three-Month Follow-Up Visit Window (105-365 days post procedure)
Class I and/or Class III AAD	Can be initiated, continued from prior to study enrollment, or increased in dose as long as the AAD is stopped on or before day 104 post procedure and subject will not be classified as a primary effectiveness failure.	If initiated a new AAD for atrial tachyarrhythmia (AF, AT or AFL of unknown origin ⁺) or taking a previously failed Class I/III AAD at a dose greater than the highest ineffective historical dose for AF/AFL/AT; subject will be classified as a primary effectiveness failure . Can be initiated, continued from blanking period, or increased in dose if drug is used NOT for the treatment of AF/AT/AFL of unknown origin ⁺ and subject will not be classified as a primary effectiveness failure. The reasons for use of Class I & III AAD other than AF are ventricular arrhythmias.
Class II and/or Class IV AAD	Can be initiated, continued from prior to study enrollment, or increased in dose and subject will not be classified as a primary effectiveness failure.	Can be initiated, continued from prior to study enrollment, or increased in dose and subject will not be classified as a primary effectiveness failure.

⁺AFL of unknown origin is defined as all AFL except those CTI dependent AFL as confirmed by 12-Lead electrocardiogram (ECG) and entrainment maneuvers in an EP study

Post procedure use of AADs guidelines:

- If Class I & III AAD is initiated through the 3-month follow-up visit window (i.e., day 0-104 post index procedure), appropriate reason for continuation of the AAD **MUST** be documented and provided in the EDC.
 - The Class I & III AAD **MUST** be discontinued before Day 104 if the AAD was not prescribed for reason of AF/AFL/AT recurrences.
- Post blanking period: New Class I & III AAD **MUST** only be initiated or dose of the previously failed Class I & III AAD **MUST** be only increased on or before day 104 post-procedure for documented AF/AFL/AT recurrences.
- **Amiodarone use:** Only maintenance dosage will be considered as the highest ineffective historical dose for amiodarone. Use of amiodarone at a dose greater than the historical highest ineffective maintenance dose through the 3-month follow-up visit window (i.e., day 0-104 post index procedure) will be considered as a primary effectiveness failure.
- Use of a Class I or III AAD that was previously not tolerated or contraindicated after the ablation will be considered a **major eligibility deviation**.

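### The AAD stop instruction in Protocol 12.1.1 makes no exception for a ventricular arrhythmia, at odds with Table 12.1.1.1, and its deadline falls one day before the Table's

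*Protocol*

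**What the plan says.** The post-procedure guidelines in Protocol section 12.1.1 open with a bullet whose scope is set by timing alone: "If Class I & III AAD is initiated through the 3-month follow-up visit window", that is, on days 0-104. It asks the site to document an "appropriate reason for continuation of the AAD". A sub-bullet then adds a mandatory stop: the drug must "be discontinued before Day 104 if the AAD was not prescribed for reason of AF/AFL/AT recurrences".

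Table 12.1.1.1, in the same section, is titled "AAD Usage and Impact on Primary Effectiveness Classification". Its days 0-104 column says that a Class I/III drug used in that window does not make the subject a failure, provided it is stopped by day 104 inclusive. Its days 105-365 column covers non-atrial use: "Can be initiated, continued from blanking period, or increased in dose if drug is used NOT for the treatment of AF/AT/AFL" of unknown origin, again without failure. It then says which uses it has in mind: "The reasons for use of Class I & III AAD other than AF are ventricular arrhythmias".

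SAP section 8.4.1.2 and the Protocol's own endpoint text define AAD failure as use for atrial tachyarrhythmia on days 105-365.

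**The concern.** The sub-bullet is a conduct rule in mandatory wording, and its only exemption is recurrence of AF, AFL or AT. A ventricular arrhythmia is not one of these. A subject who starts a Class I/III drug for a ventricular arrhythmia in the first 104 days therefore falls under the stop rule, although the Table treats continued use of such a drug as acceptable.

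This is a matter of patient management and deviation coding. A site that obeys the sub-bullet would withdraw an indicated drug because of the date. A site that follows the Table could be recorded as deviating. Section 15 of the Protocol forbids deviations except in emergencies, and a routine continuing prescription is not an emergency.

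**Working it through.** The plan gives no figure to reproduce. The check compares the texts and counts days.

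**Inputs**
- Stop rule (12.1.1, sub-bullet): starts on days 0-104; stop before day 104; exempt only if given for atrial recurrence.
- Table 12.1.1.1, days 0-104 column: stop by day 104 inclusive.
- Table 12.1.1.1, days 105-365 column: non-atrial use may be started, continued from the blanking period, or increased.
- Blanking period (Protocol synopsis; SAP sections 1 and 4): days 0-90.
- Three-month visit window (Protocol 13.5): days 76-104.
- AAD failure window (SAP 8.4.1.2): days 105-365, atrial use only.

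**Step 1: which starts conflict.** The stop rule covers 104 - 0 + 1 = 105 possible start days.
- Days 0-90 (90 - 0 + 1 = 91 start days): the Table says a ventricular drug can be continued from the blanking period, while the sub-bullet says it must stop. The conflict is direct.
- Days 91-104 (104 - 91 + 1 = 14 start days): the Table's continuation wording does not literally reach these starts. The result is still odd. A drug started on day 100 must have its last dose by day 103, yet the Table lets the same drug be started on day 105. A drug started on day 104 cannot comply at all.

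**Step 2: the deadline.**
- Sub-bullet: last permitted drug day = 104 - 1 = 103.
- Table: last permitted drug day = 104.
- Difference: 104 - 103 = 1 day.

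The failure window opens on day 105 = 104 + 1, so the Table's version adjoins it without a gap. The three-month visit may fall on day 104. A drug whose last dose is on that day meets the Table and breaches the sub-bullet.

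**Step 3: effect on the endpoint.** A drug given for a ventricular arrhythmia fails the indication test in the AAD failure definition whether it is stopped on day 103, stopped on day 104 or taken through day 365. The stop rule changes no subject's AAD failure status. The separate amiodarone bullet in the same list sets its own dose-based rule and is not part of this point.

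**Step 4: size of the group.** The documents give no rate of new ventricular antiarrhythmic use, and none is assumed here. Section 10.2 excludes subjects with LVEF below 40% (criterion 7), subjects with a pacemaker or ICD (criterion 23), and subjects known to need ablation elsewhere, with ventricular tachycardia as one example (criterion 4). These exclusions point to a very small group.

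**The case against.** The strongest reply is that the two texts do different jobs. The Table classifies the endpoint, and the sub-bullet guides conduct. The sub-bullet was probably aimed at drugs given through the blanking period without any recurrence, and its parent bullet already lets a site document a reason for continuing. On that reading a sensible site would keep a ventricular drug going.

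This is a fair account of the likely intent, but the intent is not written down. The sub-bullet follows the documented-reason clause with a mandatory stop that has one exemption. The Table's wording is permissive, so a site reading the section finds a permission and a prohibition for the same drug.

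Three parts of the reply stand in full, and each limits the point.
- A reader might infer that the Table's days 0-104 cell has the same gap. It does not. That cell states a condition for not being scored a failure, and the adjacent days 105-365 cell settles non-atrial use.
- A reader might infer that the 'Post blanking period' bullet, under which the dose of a previously failed drug may "be only increased on or before day 104 post-procedure for documented AF/AFL/AT recurrences", also bars ventricular use. Its terms are defined earlier in the section. A drug is new only "if the drug is administered to treat atrial tachyarrhythmia episodes post-enrollment", and a previously failed drug must have been given for AF. The bullet is already limited to atrial use.
- A reader might infer that the Table allows continuation of every drug started on days 0-104. Literally, it covers continuation only from days 0-90.

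**Conclusion.** The sub-bullet is wrong as written, and the consequence is small. It orders an indicated ventricular antiarrhythmic to be stopped by date while the Table in the same section allows its use, and its deadline is one day earlier than the Table's. Primary effectiveness classification does not change. What remains is patient safety and consistent deviation coding for a group that is likely very small and may be empty.

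Two larger readings are not supported.
- A reader might count the 365 - 104 + 1 = 262 days on which the sub-bullet could forbid the drug. That is a calendar ceiling for one hypothetical subject and measures no effect on the trial.
- A reader might infer that a deviation could remove a subject from the per-protocol set, in which effectiveness is tested. The definition of that set is blacked out, so the documents cannot show this.

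The conclusion rests on a literal reading of the sub-bullet and on finding nothing in the readable text that reconciles it with the Table.

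**What to change.** Reword the sub-bullet only, for example:

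> Stop the Class I/III AAD on or before Day 104 unless it was prescribed for documented AF/AFL/AT recurrence or for a ventricular arrhythmia.

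Keep the atrial-recurrence exemption, which is the sub-bullet's own, and leave failure scoring from day 105 unchanged. Apply the rule from the recorded drug indication. Under this wording, neither a ventricular drug continued past day 104 nor a stop on day 104 itself is a deviation. The Table's days 0-104 cell and the 'Post blanking period' bullet need no change.

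The cost is one sentence in a protocol amendment and a short memo to sites. Section 13.5 already collects indications and start and stop dates for cardiac drugs, so no new data, visits or patients are needed.

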	
Primary effectiveness:
 
Freedom from documented (symptomatic and asymptomatic) atrial tachyarrhythmia (AF, AT or AFL of unknown origin⁺) episodes based on electrocardiographic data (≥30 seconds on ECG or sponsor provided TTM or Holter device) during the effectiveness evaluation period (Day 91-Day 365) and freedom from the following failure modes:
 
• Acute procedural failure, including:
• Failure to confirm entrance block in all pulmonary veins (except those that are silent and/or cannot be cannulated post-procedure) at the end of the procedure• Repeat ablation failure, including:
• More than 1 repeat ablation procedures for AF/AT/ AFL (of unknown origin⁺) during the 3-Month Blanking Period (Day 0-90 post index procedure).• Any repeat ablation procedure for AF/AT/ AFL (of unknown origin⁺) during the evaluation period.• Non-study catheter failure, including:
• use of a non-study catheter (NSC) to treat pulmonary vein targets to achieve isolation of clinically relevant PVs (all PVs except those that are silent and/or cannot be cannulated) and/or to ablate left atrial non-PV AF targets during the index procedure• use of a non-study catheter to treat pulmonary vein targets to achieve isolation of clinically relevant PVs (all PVs except those that are silent and/or cannot be cannulated) during repeat procedure in the blanking period.• AAD failure:
• Taking a new AAD (Class I & III) for atrial tachyarrhythmia (AF, AT or AFL of unknown origin⁺) or taking a previously failed Class I/III AAD at a greater than the highest ineffective historical dose for AF/AFL/AT past the 3-month follow-up visit window (i.e., from day 105-365 post index procedure)• Continuous AF/AT/AFL of unknown origin⁺ on a standard 12-lead ECG during the effectiveness evaluation period.• Any DC cardioversion procedure during the evaluation period for documented atrial tachyarrhythmia (AF, AT or AFL of unknown origin⁺) recurrences ascertained through protocol specified arrhythmia monitoring methods(12-lead ECG, TTM and Holter).

⁺AFL of unknown origin is defined as all AFL except those CTI dependent AFL as confirmed by 12-Lead electrocardiogram (ECG) and entrainment maneuvers in an EP study
	

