 - More than 1 repeat ablation procedures for AF/AT/ AFL of unknown origin[†] during the 3-Month Blanking Period (Day 0-90 post index procedure).
 - Any repeat ablation procedure for AF/AT/ AFL of unknown origin during the evaluation period.

CCI

CCI

- AAD failure:
 - Taking a new AAD (Class I & III) for atrial tachyarrhythmia (AF, AT or AFL of unknown origin⁺) or taking a previously failed Class I/III AAD at a greater than the highest ineffective historical dose for AF/AFL/AT beyond the 3-month follow-up visit window (i.e., at any time from day 105-365 post index procedure).
- Continuous AF/AT/AFL of unknown origin⁺ on a standard 12-lead ECG during the effectiveness evaluation period.
- Any DC cardioversion procedure during the evaluation period for documented atrial tachyarrhythmia (AF, AT or AFL of unknown origin⁺) recurrences ascertained through protocol specified arrhythmia monitoring methods (12 lead ECG, TTM and Holter).

⁺AFL of unknown origin is defined as all AFL except those CTI dependent AFL as confirmed by 12-Lead ECG and entrainment maneuvers in an EP study.

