8.4.1.2. Primary Effectiveness Endpoint

The primary effectiveness endpoint is freedom from documented (symptomatic and asymptomatic) atrial tachyarrhythmia (atrial fibrillation [AF], atrial tachycardia [AT], or atrial flutter [AFL] of unknown origin⁺) episodes based on electrocardiographic data (≥ 30 seconds on an electrocardiogram [ECG], sponsor-provided cardiac event monitor [CEM], or Holter device) during the effectiveness evaluation period (Day 91-365 post index procedure) and freedom from the following failure modes:

- **Acute procedural failure**, defined as failure to confirm entrance block in all pulmonary veins (except those that are silent and/or cannot be cannulated post-procedure) at the end of the procedure.
- **Repeat ablation failure**, including:
 - More than 1 repeat ablation procedures for AF/AT/AFL of unknown origin⁺ during the 3-Month Blanking Period (Day 0-90 post index procedure).
 - Any repeat ablation procedure for AF/AT/AFL of unknown origin⁺ during the evaluation period.
- **Non-study catheter failure**, including:
 - Use of a NSC to treat pulmonary vein targets to achieve isolation of clinically relevant PVs (all PVs except those that are silent and/or cannot be cannulated) and/or to ablate left atrial non-PV AF targets during the index procedure.
 - Use of a NSC to treat pulmonary vein targets to achieve isolation of clinically relevant PVs (all PVs except those that are silent and/or cannot be cannulated) during repeat procedure in the blanking period.
- **AAD failure**, defined as taking a new Class I/III AAD for atrial tachyarrhythmia (AF, AT or AFL of unknown origin⁺) or taking a previously failed Class I/III AAD at a greater than the highest ineffective historical dose for AF/AT/AFL beyond the 3-month follow-up visit window (i.e., at any time from day 105-365 post index procedure).
- **Continuous AF/AT/AFL of unknown origin⁺** on a standard 12-lead ECG during the effectiveness evaluation period.
- **Any Direct Current Cardioversion (DCCV) procedure** during the evaluation period for documented atrial tachyarrhythmia (AF, AT or AFL of unknown origin⁺) recurrences ascertained through protocol specified arrhythmia monitoring methods (12-lead ECG, CEM and Holter monitor).

⁺AFL of unknown origin is defined as all AFL except those cavotricuspid isthmus (CTI) dependent AFL as confirmed by 12-Lead ECG and entrainment maneuvers in an EP study.

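### The protocol's amiodarone bullet makes higher dosing on Day 0-104 a primary effectiveness failure; its own AAD table and every visible endpoint definition do not

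*Protocol*

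**What the plan says.** **Amiodarone bullet.** Among the guidelines on AAD use after the procedure (protocol 12.1.1), the amiodarone bullet first says that only the maintenance dose counts when fixing the subject's past ineffective dose. It then says: "Use of amiodarone at a dose greater than the historical highest ineffective maintenance dose through the 3-month follow-up visit window", with the window and consequence spelled out as "i.e., day 0-104 post index procedure) will be considered as a primary effectiveness failure".

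**AAD table.** Section 12.1.1 lists the drug by name: "Class III drugs (e.g., amiodarone, dronedarone, dofetilide, etc". For Class I and III drugs on Day 0-104, Table 12.1.1.1 exempts starting, continuing or raising the dose from failure on this endpoint, under the following condition: "as long as the AAD is stopped on or before day 104 post procedure and subject will not be classified".

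**Endpoint definitions.**
- Protocol synopsis, AAD failure: "past the 3-month follow-up visit window (i.e., from day 105-365 post index procedure".
- Protocol section 9, primary effectiveness endpoint (the text before 9.2.3; its own heading is redacted): "taking a previously failed Class I/III AAD at a greater than the highest ineffective historical dose for AF/AFL/AT beyond the 3-month follow-up visit window", followed by the same Day 105-365 range.
- SAP 8.4.1.2: "beyond the 3-month follow-up visit window (i.e., at any time from day 105-365 post index procedure".

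None of the three mentions an amiodarone exception in its visible text.

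**The concern.** The bullet attaches a primary-endpoint failure to exposure in a period that the table and all three endpoint definitions leave free of AAD failure. The same subject can therefore be classified in opposite ways on the primary effectiveness endpoint, depending on which passage is applied.

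An analyst who follows the visible SAP definition has one rule. The protocol, which sites follow, states a second one, and no visible text says which prevails. The trial is single-arm and unmasked, with success judged against a fixed 50% goal, so a choice between readings made after outcomes are known would be open to the criticism that the data drove it. Conduct may also be affected: an investigator who takes the bullet at face value may withhold amiodarone in a window where the table permits it.

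**Working it through.** **1. Classification.** Take subjects who have a past ineffective amiodarone maintenance dose, exceed it after ablation for AF/AT/AFL, and have no other failure.

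| Post-ablation course | Amiodarone bullet | Table 12.1.1.1 | Synopsis, protocol section 9, SAP 8.4.1.2 |
|---|---|---|---|
| Higher dose Day 30-80, then stopped | Failure | Not a failure | Not a failure |
| Higher dose Day 30-80, then continued at no more than the past dose | Failure | Stop condition not met in the Day 0-104 column; dose criterion not met in the Day 105-365 column | Not a failure |
| Higher dose continued after Day 104 | Failure | Failure | Failure |

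The first row is the direct contradiction. In the second row the bullet still conflicts with the endpoint definitions, while the table does not settle the case. In the third row all sources agree. The guideline bullet just before the amiodarone one also contemplates raising a previously failed Class I/III drug up to Day 104 for documented recurrence, which sits badly with an automatic failure for doing so.

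**2. What one subject is worth.** The documents give no figure for this point, so there is none to reproduce. Inputs: 225 evaluable subjects (SAP 7), a 50% performance goal, and an exact binomial test at one-sided 0.025 (SAP 8.5.2). Assumption: all 225 are in the analysed set.

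- Critical count: the smallest r with P(X ≥ r | n = 225, p = 0.50) ≤ 0.025 is r = 128, which is 128/225 = 56.9%, with attained alpha 0.0226.
- Check by confidence interval: the lower bound of the exact two-sided 95% interval is 0.5014 at 128 successes and 0.4969 at 127.
- One reclassified subject: 1/225 = 0.44 percentage points.
- If only 200 were analysed, the critical count would be 115 (57.5%).

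**3. Reclassifications needed to reverse a positive result.** With s successes under the SAP rule, the result is lost when the count falls to 127, so the number needed is s − 127. The values of s are illustrations, not forecasts.

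| s | Success rate | Reclassified subjects needed | Share of 225 |
|---|---|---|---|
| 135 | 60.0% | 8 | 3.6% |
| 147 | 65.3% | 20 | 8.9% |
| 158 | 70.2% | 31 | 13.8% |

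**4. Effect on power.** The design success rate is redacted, so the true rate and the share reclassified are both assumed. Power is P(X ≥ 128 | n = 225, p − k), where k is the share of all subjects moved from success to failure.

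| True rate p | k = 0 | k = 1% | k = 2% | k = 5% |
|---|---|---|---|---|
| 60% | 84.6% | 76.2% | 65.8% | 30.8% |
| 65% | 99.5% | 98.8% | 97.5% | 84.6% |

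At a true rate of 70%, power stays at or above 99.5% for all these shares.

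**The case against.** The strongest reply is that the analysis rule is already fixed. SAP 8.4.1.2 restates the whole endpoint, agrees with the synopsis, protocol section 9 and the table, and leaves one guideline bullet as the outlier. That bullet is very likely a slip for past or beyond the window. Its maintenance-dose definition has a role in the endpoint only on Day 105-365, and the bullet before it allows increases up to Day 104. The affected group is narrow, nothing in the documents gives an amiodarone frequency, and even the smallest reversal count above (8 subjects) has no support there. Re-use of a drug that was previously not tolerated is handled separately as a major eligibility deviation. The per-protocol criteria are redacted, so whether such subjects remain in the primary test cannot be seen. Sponsor staff running the study also have no access to aggregated main-phase endpoint summaries until filing preparation (SAP 3).

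Most of this stands, and it limits the size of the problem. It does not remove it. The bullet gives its day range explicitly as 0-104, so a reader cannot safely assume a slip. A deliberate drug-specific exception is also a coherent reading, but it would then be a failure mode missing from the table and from all three definitions. Parts of SAP 8.1, 8.5.2 and 8.10 and of protocol section 18 are redacted and might say more. They would not change the conflict between the bullet and the table, which are both visible in the same protocol section.

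**Conclusion.** The concern holds: the protocol contains a stated primary-endpoint rule that contradicts its own AAD table and the visible endpoint definitions in both documents. The direct conflict covers subjects with a past amiodarone maintenance dose who exceed it on Day 0-104, stop by Day 104 and otherwise succeed. Their number is unknown and probably small. The trial's conclusion would be at risk only if the success count fell close to 128 of 225, assuming all 225 are analysed. It should be fixed because it concerns the definition of a primary endpoint and is cheap to settle, not because a large numerical effect has been shown.

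**What to change.** Change the amiodarone bullet so that failure applies beyond the three-month visit window (Day 105-365), and keep its statement that only the maintenance dose counts as the past ineffective dose. This brings it into line with the endpoint.

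If an amiodarone-specific failure on Day 0-104 is intended, add it as an explicit failure mode in Table 12.1.1.1, the synopsis, the protocol's primary effectiveness endpoint text and SAP 8.4.1.2.

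Which rule is meant is for the sponsor's clinicians to decide, before the data are read. The cost is one line of protocol wording, or one added failure mode in four places. No extra patients, visits or analyses are needed.

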10.2 Eligibility Criteria

Inclusion Criteria

Candidates for this study must meet ALL of the following criteria:

1. Symptomatic paroxysmal AF with:
 - a. At least two (2) symptomatic AF episodes within last six (6) months from enrollment
 - b. At least one (1) AF episode electrocardiographically documented within 12 months prior to enrollment. Electrocardiographic documentation may include, but is not limited to electrocardiogram (ECG); Transtelephonic monitoring (TTM), Holter monitor or telemetry strip, and
 - c. A physician's note indicating recurrent self-terminating AF within 7 days.
2. Failed at least one (1) AAD (Class I or Class III) as evidenced by recurrent symptomatic AF, intolerable side effects to the AAD, or contraindication to the AAD
3. Age 18-75 years
4. Willing and capable of providing consent
5. Able and willing to comply with all pre-, post- and follow-up testing and requirements.

Exclusion Criteria

Subjects will be excluded from the study if they meet ANY of the following criteria.

1. Previously diagnosed with persistent AF (> 7 days in duration)
2. AF secondary to electrolyte imbalance, thyroid disease, or reversible or non-cardiac cause (e.g., untreated documented obstructive sleep apnea and acute alcohol toxicity).
3. Previous surgical or catheter ablation for AF
4. Patients known to require ablation outside the PV ostia and outside the CTI region (e.g., atrioventricular reentrant tachycardia, atrioventricular nodal reentry tachycardia, atrial tachycardia, ventricular tachycardia and Wolff-Parkinson White)
5. Documented severe dilatation of the LA (LAD >50mm) antero-posterior diameter on imaging within 6 months prior to enrollment.
6. Documented LA thrombus by imaging within 48 hours of the procedure.

7. Documented severely compromised LVEF (LVEF <40%) by imaging within 6 months prior to enrollment
8. Uncontrolled heart failure or New York Heart Association (NYHA) Class III or IV
9. History of blood clotting, bleeding abnormalities or contraindication to anticoagulation (heparin, warfarin, or dabigatran),
10. Documented thromboembolic event (including TIA) within the past 12 months
11. Previous PCI/MI within the past 2 months
12. Coronary Artery Bypass Grafting (CABG) surgery within the past 6 months (180 days)
13. Valvular cardiac surgical/percutaneous procedure (i.e., ventriculotomy, atriotomy, valve repair or replacement and presence of a prosthetic valve).
14. Unstable angina within 6 months

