8.5.2 Analysis of Primary Effectiveness Endpoint

In the Pilot phase and the Pivotal roll-in phase, the primary effectiveness endpoint will be summarized descriptively as the number and percentage of subjects free from primary effectiveness failure. The SA will be used to analyze the primary effectiveness endpoint data from the Pilot phase and the Roll-In analysis set will be used to analyze the data from the Pivotal roll-in phase.

In the Pivotal main phase, hypothesis testing will be performed in the PP analysis set. Subjects with non-missing primary effectiveness endpoint (PEE) outcome data will be included in the primary

analysis. The primary effectiveness endpoint will be evaluated using the exact test for a binomial proportion at one-sided significance level of 2.5%. If the lower bound of the exact two-sided 95% confidence interval of the primary effectiveness success rate is greater than the performance goal of 50%, the study will be considered to have demonstrated effectiveness.

[REDACTED]

[REDACTED]

[REDACTED]

[REDACTED]

[REDACTED]

[REDACTED]

[REDACTED]

[REDACTED]

To investigate the robustness of the analysis result, sensitivity analyses including estimation of the primary effectiveness success rate in the mITT and All Treated analysis sets, worst-case and best-case scenario analyses, tipping point analysis, and Kaplan-Meier estimation will be performed in the PP, All Treated, and mITT analysis sets. Details are provided in Section 8.6.

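### Protocol 12.1.1 makes post-ablation use of a not-tolerated or contraindicated Class I/III drug an eligibility deviation, which could let outcome-related acts decide who is in the per-protocol effectiveness test

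*Protocol*

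**What the plan says.** - **The label.** The post-procedure AAD guidelines in Protocol 12.1.1 state that use of a Class I or III "AAD that was previously not tolerated or contraindicated after the ablation will be considered a major eligibility deviation". The sentence sets no limit on time after ablation, dose or indication.
- **Eligibility.** Inclusion criterion 2 (Protocol 10.2) requires failure of at least one Class I or III AAD, "as evidenced by recurrent symptomatic AF, intolerable side effects to the AAD, or contraindication to the AAD". All of this is known before enrolment.
- **Drug categories.** Under Protocol 12.1.1, "ANY AAD that was never taken for the treatment of AF prior to enrollment" counts as new if it is given for atrial tachyarrhythmia after enrolment. A drug stopped earlier for intolerable side effects counts as previously failed.
- **Endpoint.** SAP 8.4.1.2 has an AAD failure mode, "defined as taking a new Class I/III AAD for atrial tachyarrhythmia", or taking a previously failed Class I/III drug above its highest ineffective historical dose, on Days 105-365.
- **Deciding analysis.** SAP 8.5.2: "In the Pivotal main phase, hypothesis testing will be performed in the PP analysis set". SAP 8.5.3 makes study success depend on that test together with the safety test. The PP definition in SAP 6.2.1 is redacted.

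**The concern.** Whether a subject met inclusion criterion 2 cannot be altered by a drug prescribed after the ablation. The label nevertheless files that prescription under eligibility, the kind of deviation that a per-protocol set commonly removes. Some of the same prescriptions are primary effectiveness failures.

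The act is also tied to outcome more generally. For the post-blanking period, the same guidelines link starting a new Class I/III drug, or raising the dose of a failed one, to documented recurrence. A documented episode of at least 30 seconds from Day 91 is itself a primary failure.

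If such subjects left the PP set, failures could drop out of both numerator and denominator of the test against 50%. The observed success rate would rise and the one-sided 2.5% error rate might not hold. The secondary AFEQT test also uses the PP set (SAP 8.12), so the same exclusions would reach it. Apart from any test, deviation tables would mix enrolment errors with what happened after treatment.

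**Working it through.** **1. Which labelled acts are AAD failures?** Setting Protocol 12.1.1 and its Table 12.1.1.1 beside SAP 8.4.1.2:

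| Labelled act | AAD failure? |
|---|---|
| Contraindicated drug, never taken before, for AF/AT/AFL, Days 105-365 | Yes (new AAD) |
| Not-tolerated drug above highest ineffective historical dose for AF/AT/AFL, Days 105-365 | Yes (previously failed AAD) |
| Not-tolerated drug at or below that dose | No |
| Use stopped on or before Day 104 | No, per the table |
| Use not for AF/AT/AFL | No |

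One edge is unsettled. The amiodarone bullet in 12.1.1 counts use above the historical maintenance dose on Days 0-104 as a failure, while the table and the SAP confine AAD failure to Days 105-365. Those passages need reconciling.

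**2. The test as planned.** Inputs: 225 evaluable subjects and an exact binomial test at one-sided 0.025 (SAP 7); goal 50% (SAP 8.5.2). Let c(n) be the smallest r with P(Bin(n, 0.5) ≥ r) ≤ 0.025.

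- c(225) = 128, that is 128/225 = 56.9%, with exact lower bound 50.14%. 127/225 gives 49.69% and misses.
- Attained type I error: P(Bin(225, 0.5) ≥ 128) = 0.0226.
- The stated power, above 80%, cannot be reproduced because the assumed true rate is not visible. It holds for any true rate of at least 59.4% (84.6% at 60%).

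**3. If PP removes labelled subjects.** Assumptions: PP drops this deviation, 225 subjects before removal, true success 50%. Each failure is removed with probability f and each success with probability s. The documents give neither.

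- Probability of being retained: q = 1 − (f + s)/2.
- Success rate among those retained: π = (1 − s)/(2 − f − s).
- Type I error = Σ over m of P(Bin(225, q) = m) × P(Bin(m, π) ≥ c(m)).

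| f (failures) | s (successes) | π | Type I error |
|---|---|---|---|
| 0 | 0 | 50.0% | 2.3% |
| 1% | 0 | 50.3% | 2.5% (0.0249) |
| 2% | 0 | 50.5% | 2.9% |
| 5% | 0 | 51.3% | 4.9% |
| 2% | 1% | 50.3% | 2.4% |
| 5% | 2% | 50.8% | 3.7% |
| 2% | 2% | 50.0% | 2.1% |
| 5% | 5% | 50.0% | 2.2% |

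About 112.5 failures are expected (225 × 0.5), so f of 1%, 2% and 5% means about 1.1, 2.3 and 5.6 subjects.

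**4. Fixed counts.** Dropping one failure changes nothing: 128 of 224 are still needed. Dropping two lowers the requirement to 127 of 223, and P(Bin(225, 0.5) ≥ 127) = 0.031. A result of 127/225 (lower bound 49.69%, a miss) would become 127/223 (50.17%, a pass).

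**The case against.** The strongest reply is that no visible text says this deviation removes anyone from the PP set. The definition of a protocol deviation in Protocol section 15 does not mention analysis sets, and the redacted PP definition may already rest on pre-procedure facts. That stands. A reader might infer that the PP set does exclude these subjects and that the type I error is therefore inflated; the documents support neither step.

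A reader might also infer that all AAD use after ablation is labelled, or that the label falls almost only on failures. The wording covers only not-tolerated or contraindicated Class I/III drugs, and it catches acts that are not AAD failures, including use during blanking by subjects who may later succeed. Some of those subjects may fail through another mode, but the share is unknown. The failure-only rows above are therefore upper cases.

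Two further points have partial force. Estimates in the mITT and All Treated sets, together with worst-case, tipping-point and Kaplan-Meier analyses, are planned and might expose a gain seen only in PP, but they do not decide success. And the label may be meant as an enrolment check: later use of a drug recorded as contraindicated or not tolerated casts doubt on the evidence for inclusion criterion 2. That purpose is legitimate, but it can be served by re-checking the pre-procedure records. It does not make the later prescription an eligibility fact.

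**Conclusion.** The concern holds in limited form. The visible defect is a stated rule that gives an eligibility label to a post-ablation act, part of which is also a primary effectiveness failure, in a trial whose deciding effectiveness test uses the PP set. This creates a route to outcome-related exclusion; it does not show that such exclusion is planned.

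The size depends on whether PP uses the label, how often the act occurs, and how it divides between failures and successes. None of these is visible. Under the stated assumptions the type I error stays within 2.5% if 1% of failures alone are removed, exceeds it at 2% or 5%, rises less when some successes leave too, and is not inflated under equal removal. If PP ignores the label, the test is unaffected and only the deviation tables are muddled. The correction is still worth making because it costs almost nothing.

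**What to change.** - **Protocol 12.1.1:** class this act as a post-procedure protocol deviation, not an eligibility deviation.
- **SAP 6.2.1:** state, or confirm if the redacted text already says so, that eligibility exclusions from PP rest only on facts present before study catheter insertion. State also that post-procedure AAD use removes no subject from the PP, All Treated or mITT set and is scored under the existing AAD-failure rule.
- **Enrolment check:** where such use casts doubt on the evidence for inclusion criterion 2, re-check that evidence against pre-procedure source records.

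The cost is one phrase in the protocol and a short statement in the SAP. No drug, dose or clinical rule changes. The downside is that the reported success rate may be slightly lower.
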